### **B. Secondary**

1. To evaluate the sensation and pain during and after STAR particle application.

### **C. Exploratory**

1. To assess the dispersion and disposal of the STAR particles.
2. To evaluate the user's feedback on product use.

## **3. Background**

The objectives of this protocol are motivated by the potential future applications of STAR particles to enhance cutaneous bioavailability of topical therapies for treatment of dermatoses.

Many medical indications are treated through the topical application of a therapeutic compound that has been formulated into a gel, cream, ointment, or lotion (e.g., eczema, psoriasis, actinic keratosis, cutaneous warts, etc.) [1,2]. This is especially true in dermatology in which the skin is often the primary site of action. Topicals (i.e., drugs applied to the skin's surface) allow patients to easily self-apply these therapies without the need for painful or difficult-to-use medical technologies (e.g., hypodermic needles) or the risks associated with systemic exposure to a drug (e.g., oral, intravenous, or intramuscular administration).

Despite the advantages associated with topical delivery, the skin significantly hinders the transport of most exogenous compounds. The skin derives this functional barrier primarily from its outermost layer, the stratum corneum. The stratum corneum is approximately 10-20  $\mu\text{m}$  in thickness and is composed of denucleated, terminally differentiated skin keratinocytes which form a tightly packed lipophilic shield to the outside world [3]. To overcome the skin barrier, several techniques have been employed. Various chemical, biochemical, and physical methods have been studied to increase skin permeability [4-7]. However, chemical, and biochemical methods do not appear to be broadly useful for the delivery of large molecule therapeutics (e.g., peptides, proteins, genetic material) across the skin. While physical methods have greater promise for the delivery of macromolecules, they typically involve the use of sophisticated devices that are relatively large, expensive, and/or require training. Microneedles (MNs), in contrast, can be prepared as a low-cost patch that is simple for patients to apply for the delivery of a larger range of therapeutics [8-10]. One microneedle (MN) technique that has been investigated for enhanced topical drug delivery is called "poke-and-patch." This method most commonly employs solid, non-dissolving microneedles (MNs), which are attached to a flat or cylindrical substrate, allowing for

penetration into the skin. The MNs are then removed from the skin, thereby revealing microscopic puncture sites. Subsequently, a topical formulation can be applied to the MN-treated site, and the pharmaceutical agent can passively diffuse through the created microchannels. Although this technique has shown promise to increase transport into and across the skin, there are several drawbacks to its widespread clinical adoption. These drawbacks include: (1) training users to properly apply MNs, (2) MN device sterility between treatments, (3) MN device cost, (4) complexity of a two-step application process, and (5) the small surface area of MN patches (e.g., <10 cm^2) in relation to many relevant dermatoses.

#### **4. Study Endpoints**

##### **A. Primary**

- 1) For each primary objective, the **primary endpoint** is the identification of the most efficacious conditions measured by the number of perforations per cm^2 using GV staining and TEWL measurement before and after application of STAR particles [(T0 (before), T20 (after), T30, GV)].

##### **B. Secondary**

- 1) Evaluate the sensation and pain during and after application of STAR particle administration using questionnaires after each application.
- 2) Assess general safety objectives including standard adverse event (AE) reporting from enrollment until 5 days after the last visit.

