### **B. STAR particle application**

A 1.5 gram dose of STAR particles (10% concentration in gel) will be applied to the eight application sites (forearm and hand) and 100 mg of the gel without STAR particles will be applied to the control site on one of the forearms. Two rubbing cycles (30 and 60 cycles at a minimum of 1 cycle/second) and three pressures (40, 60, and 80 kPa) will be evaluated. The parameters of each STAR particle application at each site (1-9) are labelled in Figure 1. The investigator will apply the STAR particles with two fingers (index and middle fingers of the dominant hand) and the pressure point of one finger is 1 cm^2. Pressures have been established with the following amount of STAR particles applied to the skin with one finger: 40 kPa (320 grams); 60 kPa (480 grams); and 80 kPa (640 grams). With two fingers, the investigator will apply with a pressure of 40 kPa when scale reads 640 grams; 60 kPa = 960 grams; and 80 kPa = 1280 grams. This will be practiced enough before the study so the investigator will know how much pressure generated on the skin based on previous practice with associating pressure according to scale weight.

[figure not shown]

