#### **Application of STAR particles to volar side of each forearm (Figure 1)**

1. Wash participant's arms and hands with disinfecting soap before any application.
2. Allowed skin to dry for at least 10 minutes.
3. Investigator to delimit the 9 areas on participant's forearms and hand with a marker.
4. Measure TEWL  $T_0$  on all 9 sites - measure from areas 1 to 9 and then from 9 to 1, giving 2 measurements for each time point according to Figure 1.
5. Apply STARS (80KPa for 60 cycles) on the dorsum of the closed hand.

6. Apply STARs (80KPa for 60 cycles) to the palmar surface of the same hand.
7. Apply STARs (pressure and # of cycles) to the six areas on the forearms per Figure 1.
8. Extra care will be taken to wash arms and hand with warm water to remove the STAR particles and gel and allowed to dry at least 5 min before the next TEWL ( $T_{20}$ ) is taken.
9. Measure TEWL  $T_{20}$  on all 9 sites - measure from areas 1 to 9 and then from 9 to 1, giving 2 measurements for each time point according to Figure 1.
10. Participant completes Tolerability Questionnaire
11. Participant completes Removal & Disposal Questionnaire and User's Feedback Questionnaire.
12. Pictures (3) will be taken to assess erythema: both forearms and the hand
13. Measure TEWL  $T_{30}$  on all 9 sites - measure from areas 1 to 9 and then from 9 to 1, giving 2 measurements for each time point according to Figure 1.
14. Apply GV staining for 10 minutes on the 2 arms resting with volar arm upward and right hand on a gauze containing GV stain.
15. Wash and wipe off the GV stain thoroughly with ethanol 70%.
16. Take 3 photos of each site to visualize the puncture after GV staining.
17. Using 2 fingers (index and middle), the participant will apply pressure to a kitchen scale in an effort to mimic application of low, medium, and high pressures.
18. The investigator records the weight (from the scale) when the pressure is constant.
19. Participant is discharged.

**Figure 1:** STAR particle application sites for V1 (participants #1-10)

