**Application of STAR particles to volar side of each forearm**

20. Wash participant's arms and face with disinfecting soap before any application.
21. Allowed skin to dry for at least 10 minutes.
22. Investigator to delimit the 9 areas on participant's forearms and face with a marker.
23. Measure TEWL  $T_0$  on all 4 sites - measure from areas 1 to 4 and then from 4 to 1, giving 2 measurements for each time point.
24. Apply STARs (80KPa for 60 cycles) on the forearm.
25. Apply STARs (80KPa for 60 cycles) to the side of the face.
26. Apply gel without STARs on the other forearm and on the other side of the face.
27. The study team will take photos of the application sites.
28. After approximately 5 minutes, the gel (with or without STAR particles) will be removed with a dry tissue or gauze.
29. The study team will take photos of the areas of application.
30. After the gel is removed in all areas, the investigator will examine the participant to check if there are any remaining STAR particles on the participant and/or the surrounding environment.
31. Participant completes Tolerability Questionnaire
32. Participant completes Removal & Disposal Questionnaire and User's Feedback Questionnaire.
33. Pictures (3) will be taken to assess erythema: both forearms and the face
34. Measure TEWL  $T_{30}$  on all 4 sites - measure from areas 1 to 4 and then from 4 to 1, giving 2 measurements for each time point.
35. Apply GV staining for 10 minutes on the 2 arms resting with volar arm upward and right hand on a gauze containing GV stain.
36. Wash and wipe off the GV stain thoroughly with ethanol 70%.
37. Take 3 photos of each site to visualize the puncture after GV staining.
38. Using 2 fingers (index and middle), the participant will apply pressure to a kitchen scale in an effort to mimic application of low, medium, and high pressures.
39. The investigator records the weight (from the scale) when the pressure is constant.
40. Participant is discharged.

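### Pain and sensation are to be rated after each application, but the step lists schedule one questionnaire after all sites have been treated

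*Protocol*

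**What the plan says.** The sole secondary objective in Section 2.B is "To evaluate the sensation and pain during and after STAR particle application". Section 4.B.1 turns it into an endpoint: "Evaluate the sensation and pain during and after application of STAR particle administration using questionnaires after each application". Section 6.C uses the word application for the treatment of one site, giving eight STAR applications and one control per person. Section 6.B sets the conditions under study: "Two rubbing cycles (30 and 60 cycles at a minimum of 1 cycle/second) and three pressures (40, 60, and 80 kPa").

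For participants 1-10 the order in Section 6.C is:

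- Step 5: "Apply STARS (80KPa for 60 cycles) on the dorsum of the closed hand".
- Step 6: the palm of the same hand, at the same setting.
- Step 7: STAR particles "to the six areas on the forearms per Figure 1".
- Step 8: washing, after which the skin is "allowed to dry at least 5 min before the next TEWL" reading.
- Step 9: T20 TEWL on nine sites, each measured twice.
- Step 10: "Participant completes Tolerability Questionnaire".

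For participants 11-20 (Section 6.D), STAR particles go on one forearm and one side of the face, and plain gel on the opposite sides (steps 24-26). Step 28 follows: "After approximately 5 minutes, the gel (with or without STAR particles) will be removed with a dry tissue or gauze". After photographs and a check for residual particles, the only Tolerability Questionnaire is step 31.

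The visual analog pain scale (VAPS) is defined among the abbreviations in Section 1 and has a row, shared with disposal, in the Section 9 schedule. No step in Section 6 names it.

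**The concern.** The endpoint definition asks for a rating tied to each application. The procedures give one sitting after all of them. In the first cohort, that sitting asks a person to look back over up to eight STAR sites treated at different pressures and cycle counts, after the skin has been washed, dried and measured.

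If staff work from the step list, pain during application is never recorded during or directly after it, and telling which setting hurt depends on memory. Tolerability by setting is useful information when Section 5 allows pressure or rubbing cycles to change after ten participants, although the Protocol does not say that pain will drive that decision. This is a matter of data collection: an analysis plan cannot restore a rating that was not taken at the time.

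**Working it through.** The Protocol gives no statistical figure here to reproduce. The check is a count of rating occasions, a reading of the time order, and an illustration of the delay.

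**1. Rating occasions per participant**

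| | Participants 1-10 | Participants 11-20 |
|---|---|---|
| Applications by site | 8 STAR + 1 control = 9 | 2 STAR + 2 control = 4 |
| Ratings implied by Section 4.B.1 | 8 (STAR only) or 9 | 4 |
| Tolerability Questionnaires scheduled in Section 6 | 1 (step 10) | 1 (step 31) |

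The second column follows steps 24-26, since the opening sentence of Section 6.D speaks of eight applications but describes four.

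**2. Where VAPS falls.** The Section 9 rows run T20 TEWL, questionnaires, VAPS with disposal, erythema photograph, T30 TEWL. This matches the order of steps 9 to 13. The table therefore places VAPS with the questionnaires, after T20. It does not say how many scores are taken per site.

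**3. Delay fixed by the Protocol.** In participants 1-10, every site waits through the wash, at least 5 minutes of drying and 9 x 2 = 18 TEWL readings. The delay is thus more than 5 minutes for every site. In participants 11-20 it is about 5 minutes plus removal, photographs and inspection.

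**4. Illustration for the first-treated site, participants 1-10.** Assume the six forearm sites form the full grid of 3 pressures x 2 cycle counts (Figure 1 is not shown).

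- Hand: 2 x 60 = 120 cycles.
- Forearms: 3 x 30 + 3 x 60 = 270 cycles.
- Total: 120 + 270 = 390 cycles. After the first site: 390 - 60 = 330.
- At 1 cycle/s, the slowest rate allowed: 330 s = 5.5 min. With drying: 5 + 5.5 = 10.5 min.
- At an assumed 2 cycles/s: 165 s = 2.75 min. With drying: 5 + 2.75 = 7.75 min.

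Washing, changeovers and TEWL come on top, with no stated duration. Section 6.B sets a minimum rate and no maximum, so 7.75 minutes is an example, not a lower bound.

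**5. Settings to be told apart.** Under the same grid assumption, one sitting in participants 1-10 covers 3 x 2 = 6 different settings over eight sites, because both hand sites repeat 80 kPa with 60 cycles. In participants 11-20 both STAR sites receive 80 kPa with 60 cycles, so there is one setting and nothing to confuse.

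**The case against.** The strongest reply is that Section 6 omits a per-site rating without forbidding one. A reader might infer that staff cannot follow both sections. The text does not go that far: staff could rate after each site and still complete step 10. What stands is that no step tells them to.

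It can also be said that application sometimes means the whole session, as in the opening of Section 6 and the single schedule row. But Section 6.C counts applications by site, and with one visit the word each in Section 4.B.1 would have no work to do on the session reading.

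The Tolerability Questionnaire is not shown and may ask about each site separately. That would give site-level answers and soften the attribution problem. It would not make them answers given after each application.

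A reader might also infer that VAPS has no timing at all. The row order in Section 9 implies one, after T20; only the number of scores is open.

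Finally, Section 19 lets the participant or the PI stop during application for discomfort or pain, and one might conclude that such a person would have no pain score. The Protocol does not say that steps 10 and 31 lapse after a stop. Section 19 also has participants report observations during the procedure, and two discomfort stops halt the study. What remains is a small gap: no step asks for a score at the moment of stopping.

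**Conclusion.** The mismatch between Section 4.B.1 and Section 6 is real and should be corrected. Its size is one scheduled rating occasion against eight or nine implied in participants 1-10, and against four in participants 11-20, with a delay of more than 5 minutes in the first cohort and about 5 minutes or more in the second.

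The consequence differs by cohort. In participants 1-10, attribution of pain to a pressure or cycle setting is weakened, even if the form asks site by site. In participants 11-20 only the recall delay applies. It would be wrong to claim a known bias: no pain values or stopping rates are given.

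The count rests on reading application as site-level. The figure of six settings and the 7.75 to 10.5 minute illustration rest on the assumed forearm grid, and the shorter time also on an assumed 2 cycles/s. The matter concerns a secondary endpoint in a 20-person pilot, and it is cheap to put right.

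**What to change.** 1. In Section 6, for both cohorts, record one VAPS pain score immediately after each site's application, control sites included. The participant marks or points to the scale, so that it remains a visual analog score.
2. Keep the questionnaires at steps 10 and 31 for sensation and for the rating after application.
3. Reword Section 4.B.1 to match: VAPS after each application, Tolerability Questionnaire once after all applications.
4. In Section 9, list VAPS per site alongside STAR particle application.
5. As a minor addition, if application is stopped for discomfort or pain, record the score then for the site in progress.

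The cost is a few sentences, one schedule row and one case report form line per site. The drawback is added time before post-application TEWL and GV staining, which serve the primary endpoint. At an assumed 5-15 s per score:

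- Participants 1-10, STAR sites only: 8 x 5-15 s = 40-120 s for the first site, and the gap between first and last site grows by 7 x 5-15 s = 35-105 s.
- Participants 1-10, with the control site: 9 x 5-15 s = 45-135 s, and the gap grows by 8 x 5-15 s = 40-120 s.
- Participants 11-20: 4 x 5-15 s = 20-60 s.

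For comparison, rubbing alone makes the first-to-last gap 165-330 s under the assumptions above. The score should therefore be a single quick mark and not the full questionnaire.

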##### **C. Exploratory**

- 1) Perform a visual inspection of the residual STAR particles to assess potential adverse events after removal.
- 2) To evaluate the user's feedback using a specific questionnaire.

#### **5. Study Intervention/Investigational Agent**

This is a non-randomized, controlled, non-blinded, single-arm pilot study trial, with an adaptive design at mid-trial. After 10 participants complete the study, an interim analysis will be performed and recruitment will either continue with no change to the protocol or, changes may occur in regard to the STAR particle application area, position, pressure, or rubbing cycle in an adaptive design manner.

The trial will be performed in a climatized room and participants will have time to adapt and cool down to decrease risk of modulation TEWL reading.

The investigational agent will be STAR particles made of titanium dioxide, a widely used and safe ceramic material found in sunscreens, cosmetics, and paint. The star-shaped geometry is designed to inhibit complete insertion of the particle into skin, so STAR particles do not remain embedded in the skin. After the arms of the STAR particle puncture the skin, the elastic forces of the skin push the particles out. The STAR particles will be mixed with a gel formulation of the following composition: 0.7%w/w Xanthan Gum + 2.5%w/w Hydroxypropyl methylcellulose + Cyclomethicone and Dimethicone. STAR particles will be produced by Aldena Therapeutics under GMP conditions.

## **6. Procedures Involved**

After signing the informed consent form, eligible healthy adult participants will be enrolled in the study. The study will require one clinic visit. The visit will serve as a screening visit in order to explain the study, review inclusion/exclusion criteria, assess the participant's skin, and perform the STAR particle application. The study visit will last approximately two hours.

### **A. Study visit**

- 1) Review study
- 2) Assess participant skin
- 3) Obtain Consent
- 4) Apply STAR particles

### **B. STAR particle application**

A 1.5 gram dose of STAR particles (10% concentration in gel) will be applied to the eight application sites (forearm and hand) and 100 mg of the gel without STAR particles will be applied to the control site on one of the forearms. Two rubbing cycles (30 and 60 cycles at a minimum of 1 cycle/second) and three pressures (40, 60, and 80 kPa) will be evaluated. The parameters of each STAR particle application at each site (1-9) are labelled in Figure 1. The investigator will apply the STAR particles with two fingers (index and middle fingers of the dominant hand) and the pressure point of one finger is 1 cm^2. Pressures have been established with the following amount of STAR particles applied to the skin with one finger: 40 kPa (320 grams); 60 kPa (480 grams); and 80 kPa (640 grams). With two fingers, the investigator will apply with a pressure of 40 kPa when scale reads 640 grams; 60 kPa = 960 grams; and 80 kPa = 1280 grams. This will be practiced enough before the study so the investigator will know how much pressure generated on the skin based on previous practice with associating pressure according to scale weight.

[figure not shown]

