### 1. Study Summary

Project Title	Usability of STAR particles in healthy volunteers: A pilot study
Project Design	Non-randomized, controlled, non-blinded, single-arm pilot (feasibility) study, with an adaptative design at mid trial.
Primary Objective	To identify the most efficacious pressure of administration and the minimum number of rubbing cycles necessary to perforate the stratum corneum.
Secondary Objective(s)	To evaluate sensation and pain during and after STAR particle application.
Exploratory Objective(s)	To assess the dispersion and disposal of the STAR particles. To evaluate the user's feedback on product use.
Research Intervention(s)/Interactions	STAR particles STAR particles are millimeter-scale particles with micron-scale projections made of biocompatible materials that painlessly disrupt the stratum corneum. As STAR particles are rubbed on skin, their microscopic projections create micron-scale pores in the stratum corneum to increase skin permeability to topical compounds independent of physicochemical properties. After the arms of the STAR particle puncture the skin, the elastic forces of the skin push the particles out. Participants will receive the 8 interventions (different application pressures) plus the control (Site and treatment will not be randomly assigned on the arm) by the investigator.
Study Population	Adults (18 to 39 years of age)
Sample Size	20
Study Duration for individual participants	1 visit to screen for medical history, examine skin, obtain informed consent, and application of the STAR particles to the participant's forearm.
Study Specific Abbreviations/ Definitions	GV – Gentian Violet; kPa - kilopascal; microneedle (MN); TEWL – trans epidermal water loss; VAPS – visual analog pain scale
Funding Source (if any)	Aldena Therapeutics (United Kingdom)
Study Site	Emory Children's Center

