### **C. Participants 1-10**

Enrolled healthy adults will receive eight applications (three on each forearm and two to one hand) of STAR particles and one control application on the volar side of one of the forearms for a total of nine applications to the forearms. In addition, two applications of STAR particles will be applied to one of the hands – one application to the palmar surface and one to the dorsum of the hand (Figure 1).

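### In participants 1-10 the gel-only control site appears to receive less gel than each STAR site, so a STAR-versus-control TEWL contrast mixes particles with amount of gel

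*Protocol*

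**What the plan says.** Section 6.B sets both amounts in one sentence. For the active sites: "A 1.5 gram dose of STAR particles (10% concentration in gel) will be applied to the eight application sites". For the control: "100 mg of the gel without STAR particles will be applied to the control site". No reason is given for the different control amount, and no other section states another one.

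Section 6.C describes the sites for participants 1-10: "eight applications (three on each forearm and two to one hand) of STAR particles and one control application on the volar side". TEWL is read at T0, T20 and T30 "on all 9 sites - measure from areas 1 to 9 and then from 9 to 1, giving 2 measurements for each time point", so the control is measured alongside the STAR sites. The primary endpoint in section 4.A is the "number of perforations per cm 2 using GV staining and TEWL measurement before and after application of STAR particles". The Study Summary calls the design "Non-randomized, controlled, non-blinded, single-arm pilot (feasibility) study, with an adaptative design at mid trial". For participants 11-20 (section 6.D) particle-free gel goes on the opposite forearm and the opposite side of the face, and no mass is given for either side.

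**The concern.** In participants 1-10 the gel-only site is the only control. It is most useful if it differs from a STAR site in the particles alone. If it also carries less gel, a difference between the two has two possible causes. The vehicle contains cyclomethicone and dimethicone, so the amount applied could plausibly affect hydration, residue and lubrication, and through them TEWL and what the participant feels. At stake is the reading of any statement of the form: TEWL rose more under STAR particles than under gel alone. The unclear meaning of 1.5 g is a second problem, because the amount of particles per site cannot be recovered from the text.

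**Working it through.** **Inputs.** STAR dose 1.5 g at 10% in gel (6.B). Control 100 mg of gel (6.B). STAR sites 3 + 3 + 2 = 8 (6.C), which with one control makes the nine sites of the TEWL steps. I assume that 10% is by weight, so 90% of the product is gel. The protocol derives neither mass, so there is no stated figure to reproduce.

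**Formulas.** With P mg of product per STAR site: gel = 0.9 × P; product ratio = P / 100; gel ratio = 0.9 × P / 100. The gel ratio is the relevant one, since the suspected confounder is gel.

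**Results, assuming equal amounts at the eight sites.**

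- 1.5 g of product, shared: P = 1,500 / 8 = 187.5 mg; gel 168.75 mg; product ratio 1.875; gel ratio 1.69.
- 1.5 g of product per site: P = 1,500 mg; gel 1,350 mg; product ratio 15; gel ratio 13.5.
- 1.5 g of particles, shared: 1.5 / 0.10 = 15 g of product; P = 15,000 / 8 = 1,875 mg; gel 1,687.5 mg; product ratio 18.75; gel ratio 16.9.
- 1.5 g of particles per site: P = 15,000 mg; gel 13,500 mg; product ratio 150; gel ratio 135.

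**Reverse check.** Sharing 1.5 g of product equally at 100 mg per site would need 1,500 / 100 = 15 sites; there are 8. The product per STAR site spans 15,000 / 187.5 = 80-fold across the four readings.

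**Area.** Site areas are not in the text and Figure 1 is not shown. Equal gel per cm² would need a control area of 100 / 168.75 = 59% of a STAR site under the first reading, or 100 / 1,350 = 7% under the second.

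**Which comparisons depend on the control amount.**

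- Pressures and cycles among STAR sites: no, the control does not enter.
- Change from T0 within a STAR site: no.
- GV perforation counts: probably little. Nothing in the document suggests that the amount of blank gel perforates skin.
- TEWL at STAR sites against the control site: yes.
- Tolerability, if compared with the control: yes.

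**The case against.** The strongest objection is that the primary objective does not need this control. It asks for the best pressure and the minimum number of cycles, which are comparisons among STAR sites and against each site's own baseline, and the protocol specifies no STAR-minus-control difference. This stands. A reader might infer that the unequal amounts undermine the primary endpoint as a whole; the document does not support that.

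A second objection is that the eight sites need not receive equal shares. Six forearm sites at 100 mg and two hand sites at 450 mg also add up to 1,500 mg, and would match the forearm control on product. This is possible arithmetically, so one cannot say that every conceivable reading gives the STAR sites more. Nothing in the text points to such a split, however.

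Third, what matters is amount per unit area, and Figure 1 may show the areas. That stands as a limit on certainty. The control would have to be the markedly smaller site, which the text does not suggest.

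Fourth, for participants 1-10 the protocol requires careful washing with warm water and at least 5 minutes of drying before T20, and T0 is taken at all nine sites. Both reduce a bias from residue; neither is shown to remove it.

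Finally, a reader might carry the mismatch over to participants 11-20. With no mass stated on either side there, none is shown.

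**Conclusion.** The point holds within limits. As written, and assuming an equal split or a per-site dose, each STAR site in participants 1-10 receives at least 1.7 times the control's gel (1.9 times on total product), and 13.5 times if 1.5 g of product is per site. A STAR-versus-control contrast in TEWL, or in tolerability, therefore confounds particles with amount of gel. The resulting bias in TEWL cannot be quantified from the document. The ranking of pressures and cycles is untouched. The conclusion rests on equal allocation among STAR sites, 10% by weight, and site areas that do not happen to offset the difference in mass. Separately, and without any of these assumptions, the wording leaves open whether 1.5 g is product or particles, and total or per site.

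**What to change.** In section 6.B, reconcile the STAR and control amounts. State whether 1.5 g refers to product or particles, and whether it is the total over eight sites or the amount at each. If the total is divided unequally between forearm and hand, state the division. Make the vehicle amount per unit area the same at the control and STAR sites, at whatever amount the sponsor intends; which of the stated amounts should change is for the sponsor to decide. In section 6.D, state the amount for both sides in the same matched way. If a different control amount is deliberate, give the reason and do not attribute STAR-versus-control TEWL differences to the particles alone.

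The cost is one sentence in the protocol and possibly a little more blank gel per participant. No visit, measurement or sample size changes.

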## **2. Objectives**

### **A. Primary**

1. To identify the most efficacious pressure of administration and minimum number of rubbing cycles necessary for STAR particles to penetrate the stratum corneum.

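### The stated contact area (1 cm² per finger), scale targets and kPa labels in Section 6.B cannot all be right, so the absolute pressure the trial reports is in doubt by up to 21.5%

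*Protocol*

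**What the plan says.** The primary objective (Protocol Section 2.A) begins "To identify the most efficacious pressure of administration and minimum number of rubbing cycles". Section 6.B sets up the pressure factor: "three pressures (40, 60, and 80 kPa) will be evaluated". The investigator applies the particles with two fingers and learns the pressure beforehand by practising against a scale. Three statements define that calibration:

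- Contact area: "the pressure point of one finger is 1 cm", with a superscript 2, so 1 cm² per finger.
- One-finger targets: "40 kPa (320 grams); 60 kPa (480 grams); and 80 kPa (640 grams").
- Two-finger targets: a "pressure of 40 kPa when scale reads 640 grams; 60 kPa = 960 grams; and 80 kPa = 1280 grams".

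The labels are then used as settings. In Section 6.C, steps 5 and 6 use 80 kPa on the hand, and step 7 takes the forearm settings from Figure 1. In Section 6.D, step 24 reads "Apply STARs (80KPa for 60 cycles) on the forearm", and step 25 uses the same setting on the face. The text gives no other contact area, and it describes no measurement of pressure during application.

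**The concern.** A weight on a scale becomes a pressure only through the contact area. Section 6.B gives weight, area and pressure together, and the three do not agree. At least one of the printed figures is therefore wrong.

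This matters because the primary objective asks for a pressure, so the kPa value of the chosen setting is something the trial will report. The scale conversion in Section 6.B is the only link between what the investigator does and that value. If the stated area is correct, a later study or device that takes over only the kPa figure would apply more pressure than was tested here. The question also affects how the 80 kPa setting used for participants 11-20 is described.

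**Working it through.** **Inputs from Section 6.B.** Area A = 1 cm² = 1 × 10⁻⁴ m² per finger. One-finger targets are 0.320, 0.480 and 0.640 kg; two-finger targets are 0.640, 0.960 and 1.280 kg. Labels are 40, 60 and 80 kPa.

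**Input from outside the protocol.** Standard gravity, g = 9.80665 m/s².

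**Formula.** P = m × g / A.

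**Step 1: try to reproduce the labels from the stated area.**

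- 0.320 × 9.80665 / 10⁻⁴ = 31.38 kPa (label 40)
- 0.480 × 9.80665 / 10⁻⁴ = 47.07 kPa (label 60)
- 0.640 × 9.80665 / 10⁻⁴ = 62.76 kPa (label 80)

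The labels are not reproduced. The two-finger targets over 2 cm² double both force and area, so they give the same three values.

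**Step 2: size of the gap.** 31.38/40 = 47.07/60 = 62.76/80 = 0.7845, so each level is 1 − 0.7845 = 21.5% below its label. In kPa the gaps are 8.6, 12.9 and 17.2. Seen from the other side, 80/62.76 = 1.275, so a true 80 kPa would be 27.5% more than the pressure delivered.

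**Step 3: could another reading rescue the figures?**

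- Rounding g to 10 gives 32, 48 and 64 kPa, still 20% low.
- Two fingers sharing 1 cm² in total gives 62.8, 94.1 and 125.5 kPa, which does not match either.

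**Step 4: what area do the labels imply?** A = m × g / P = 0.320 × 9.80665 / 40,000 = 0.7845 × 10⁻⁴ m², or 0.7845 cm². The other two levels give the same area. A circle of 1 cm diameter has area π/4 = 0.7854 cm², and on that area:

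| One-finger target | On 1 cm² | On 0.7854 cm² | Label |
|---|---|---|---|
| 320 g | 31.38 kPa | 39.96 kPa | 40 kPa |
| 480 g | 47.07 kPa | 59.93 kPa | 60 kPa |
| 640 g | 62.76 kPa | 79.91 kPa | 80 kPa |

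The match with a 1 cm diameter is within 0.2% at every level.

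**Step 5: what weights would the labels need on 1 cm²?** m = P × A / g = 407.9, 611.8 and 815.8 g for one finger, or about 816, 1224 and 1632 g for two.

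**Step 6: effect on the comparison.** The discrepancy is one constant factor. The levels stand in the ratio 1 : 1.5 : 2 under either area and remain distinct, with steps of 15.7 kPa (1 cm²) or 20 kPa (0.785 cm²).

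**The case against.** The strongest reply is that this is a loosely worded area and nothing more. The near-exact fit to a 1 cm diameter suggests the weights were calculated correctly and the area was then misdescribed, or rounded to a whole number. The investigator practises to scale readings that are stated outright, and no procedural step uses the area. The ranking of settings is unaffected, and 80 kPa means the same 1280 g in both cohorts, so they remain comparable. If 1 cm² is literally true, the pressure is lower than labelled, which raises no safety concern. Pressure on the skin is applied by practised feel in a 20-person pilot, so the kPa values are nominal. Harm would require a later user to take the kPa value and ignore the published weights.

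Most of this stands, and it limits the point to the absolute pressure. It does not remove it. The diameter reading is an inference that the text neither states nor supports elsewhere. Calling the area rounded still leaves a printed figure that gives the wrong pressure when used for the conversion it accompanies. Variation from applying pressure by feel is a separate matter: a fixed conversion error is systematic and does not average out over participants. Figure 1 was not available in the text reviewed. Had it carried a different area, the wording of Section 6.B would still need correcting.

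**Conclusion.** The concern holds. The area, the weights and the labels in Section 6.B are mutually inconsistent at all three levels. The error in the reported pressure lies at one of two ends. It is practically nil (under 0.2%) if the contact is a circle 1 cm across and only the area is misstated. It is 21.5% at every level if the area really is 1 cm². The first is the more plausible, but the protocol does not settle it.

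The conclusion rests on standard gravity and on the whole scale reading acting over the stated contact area. It does not touch the within-trial comparison, the choice of best setting or the force actually applied. It is worth correcting because it concerns the unit of the primary result and is cheap to resolve, but it does not threaten the trial.

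**What to change.** Determine the fingertip contact area actually used and state it in Section 6.B. Then:

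- If it is about 0.785 cm² (1 cm diameter), correct the area and leave labels and weights alone.
- If it is 1 cm², either relabel the settings as about 31, 47 and 63 kPa, or change the targets to about 408, 612 and 816 g for one finger and 816, 1224 and 1632 g for two.

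Carry any change of label or target through Figure 1, steps 5-7 in Section 6.C and steps 24-25 in Section 6.D. Report each setting as scale reading plus contact area, with kPa derived from them. Steps 18 and 39 record the participants' own pressing as a weight ("The investigator records the weight (from the scale) when the pressure is constant"), so those data are unaffected; if they are ever expressed in kPa, state the area used.

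The cost is one contact-area check and a wording correction, with relabelling only in the second case. Changing the targets instead of the labels would also mean repeating the investigator's scale practice. No extra participants or visits are needed.
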